11.0 Vulnerable Populations*

11.1 It is likely that some participants may be elderly. It is also possible that some participants will be from an economically disadvantaged background, especially if partnering with a Federally Qualified Health Center such as Little Rivers, Healthcare, Inc. We feel that the payment amounts we plan to provide are appropriate given the participants' time involved and are not excessive or coercive.

PROTOCOL TITLE: *Screen to Save 2*

As stated in Section 10, our study is not targeting any of the following vulnerable populations: pregnant women, neonates/non-viable neonates, prisoners, people who have not attained legal age to consent, or cognitively-impaired adults.

12.0 Local Number of Subjects

Our target recruitment size is 196-225 people completing the pre/post survey.

13.0 Recruitment Methods

13.1—13.4

For online recruiting, we will purchase advertisements on Facebook, which will be targeted to people who meet the age and geographic eligibility criteria for study participation. We will rely of Facebook's algorithms to direct our recruitment messages to individuals in the appropriate age range and geographies. Advertisements will use verbiage such as:

“Researchers are looking for adults ages 45-74 to participate in a study about cancer screening. Residents of nine rural counties can enroll. Your voluntary and confidential participation will include reading information, watching a video, and answering survey questions. You will receive a gift card for your time. Click to learn more about participating in this research study by the Dartmouth- Cancer Center. ”

See Recruitment Messaging document attached, and see attached Sample Images that may accompany the online recruitment text.

Additionally, we may post similar advertisements on other social media platforms such as Instagram and we may post the study announcement on the DCC and/or Dartmouth Health Facebook pages. Announcements posted on the DCC and/or Dartmouth Health Facebook pages would be visible to viewers of any age and geography, as the geotargeting features of Facebook Advertising would not apply, but only those people who meet the eligibility criteria based on their responses to the screening questions would be enrolled.

In addition, we have partnered with the study team administering Study00031200 (DHH IRB) / D20039 (OnCore): Education about Health and Cancer Study to assist with identifying prospective participants for our study. That study educates online adults (from the same nine New Hampshire and Vermont counties as we are targeting in this study) about cancer research studies and clinical trials, and that study is pre-screening their study participants for possible eligibility for other studies (such as ours). As part of their participation in that study, participants will be asked some questions to see if they may be

PROTOCOL TITLE: *Screen to Save 2*

eligible to enroll in any active research studies. Screen to Save 2 will be one of the studies to which participants can be linked. Participants indicating that they are 45-74 years old will be provided with a brief description of the Screen to Save 2 study and asked for permission to share their contact information with the Screen to Save 2 study team. (See attached Recruitment Language document.) Those who give permission will have their contact information passed on to a designated Screen to Save 2 study team member, who will send an email to the STUDY00031200/D20039 participant about the Screen to Save 2 study. That email will contain a link to access the online Screen to Save 2 study. The email will also contain contact information for a Screen to Save 2 study team member, should the recipient have any questions or concerns. (See Sample Email for Participants Referred from Study D20039).

13.5 Participants will receive up to a total of \$30 in gift cards (e.g. to Amazon.com). Participants will receive a \$15 gift card for completing the pre-test, in-person or online learning, post-test, screening assessment questions (for online participants), and providing their contact information. Participants asked to complete the 3-month follow-up survey will receive an additional \$10 gift card for their time completing that survey. Participants asked to complete the 6-month follow-up survey will receive the final \$5 gift card for their time completing that survey.

The first gift card will be distributed to in-person participants in-person on the day of the event; the second and third gift cards will be sent by email, unless a participant does not have an email address or requests that the gift card be sent via regular mail; we will aim to distribute these gift cards/codes within 2 weeks of receiving completed surveys. For online participants, all gift cards will be distributed via email. Gift cards will be sent within 2 weeks of the study team receiving each completed survey.

Participants will have 6 calendar months to claim their electronic gift cards from the time that they are emailed to participants. Electronic gift cards that are not claimed after 6 months may be deactivated.

14.0 Withdrawal of Subjects*

14.1 Study subjects will be withdrawn from the study if they do not complete the pre-test, educational intervention, post-test, and provision of contact information—as we need the full set of information in order to evaluate our intervention. Additionally, as noted in Section 6, our study team will reach out to participants up to four times by email/phone (total) and up to one paper mailing for the three-month follow up survey and for the six-month follow-up survey. If no response is garnered, efforts to reach participants for the survey will be discontinued. Participants who do not respond to any of these efforts within 1.5 months of the first effort being made for that survey will be withdrawn from the study. Participants who do not complete the three-month survey will be disqualified from continuing on to the six-month follow-up survey.

PROTOCOL TITLE: *Screen to Save 2*
14.2

Any participant can discontinue participation at any time by closing the window on their device's screen that contains our video/module or survey content. Because participant contact information will be collected only after the post-test is administered, individuals who do not complete the pre-test, video/web education, and post-test will not be eligible to receive a \$15 gift card, except in instances where individuals report to the study team that they have enrolled as participants but were unable to complete the pre/post survey, despite their eligibility and intent to do so, for reasons attributable to an implementation error or substantive inconvenience in survey delivery (e.g. participant reports being unable to progress to the end of the survey). In this case, if the source of the problem cannot be remedied conveniently to facilitate completion of the survey, the \$15 gift card will still be offered, so long as the information reported to the study team appears credible, given the study team's knowledge of the eligibility criteria, recruitment strategies, study content, and technology platforms. In this case, a designated study team member will still need to collect the individual's name and contact information so that the gift card can be distributed and proper financial records maintained; however, subsequent participation in the three and six month follow-up surveys will not be allowed. Individuals who report inability to complete the survey, whose reported participation began on or after October 8, 2020, will be informed of the opportunity to receive this compensation in accordance with the standards stated above.

Any participant who does not complete the pre-test, video/web education, and post-survey will not be contacted for 3- or 6-month follow-up.

Participants who do not respond to initial communications for three- and six-month follow-up surveys will be informed, at a minimum, in the final communication effort, of the deadline by which they must respond and complete the survey in order to remain in the study. Participants in telephone-based three- or six-month follow-up surveys who express a desire to withdraw from the study partially through the survey process will be provided a gift-card, but not contacted for six-month follow-up. Participants in the online three- and six-month surveys who withdraw from the study will only receive a gift card if they have submitted the specified online survey to the study team, again with the exception that participants will be compensated for the specified survey in the event that they are eligible and intend to complete the study but report to the study team that they are unable to do so for reasons attributable to an implementation error or substantive inconvenience in survey delivery, as described above for the pre/post survey.

15.0 Risks to Subjects*

PROTOCOL TITLE: *Screen to Save 2*

15.1 Because this activity is primarily educational and seeking to increase knowledge and positive behavior change in relation to colorectal cancer and lung cancer, risks are minimal. However, some participants with a family history of cancer or who have had negative experiences with past cancer screenings may have some discomfort with the topic of colorectal cancer or lung cancer and may be distressed by the nature of the survey questions. Additionally, as with the collection of any identifiable information, there is minimal risk that confidentiality could be breached. However, we will have several safeguards in place, as described in Section 17 and in the attached document entitled *Screen to Save Data Collection Storage and Security*.

Because the risks are unlikely and minimal, we feel that they're reasonable in relation to the knowledge that participants will gain, as well as the knowledge that NCI/CRCHD and DCC will gain.

15.2-15.4. N/A

16.0 Potential Benefits to Subjects*

16.1 We do not expect a direct benefit to participants. However, participants may learn new information about cancer screening. Participants who have never discussed cancer screening with a healthcare professional, participants who have never pursued cancer screening, and participants who do not have personal or family histories of cancer may be more likely to find that the information is new to them.

By attending our in-person education events people may also have the opportunity to speak with local healthcare providers about cancer screening or other topics, regardless of whether or not they enroll in our study.

As feasible, participants will receive tailored educational information based on their individual responses to the screening option assessment and pre-test, as well as information about locally-available screening services.

17.0 Data Management* and Confidentiality

17.1. Our sample size is based on a two-tailed test with 0.05 significance level, and 80% power to detect an effect size of 0.2 (20% difference in the before/after difference-in-difference estimates), with a standard deviation of 1.0. We will conduct various statistical tests on the data to determine whether participants experienced changes in knowledge, attitudes, behavioral intentions, and behavior as a result of the intervention, and changes will be look at across groups.

17.2. To ensure confidentiality of data, we will have several safeguards in place:

- Training: All research team members with access to study data will be trained on all procedures related to data management under this protocol.
- Access restrictions: Access to electronic research materials/data will be limited to those on the research team. This will include only granting electronic access to Qualtrics and One Drive/Sharepoint to study team

PROTOCOL TITLE: *Screen to Save 2*

members, these sites/applications also require passwords to access. All laptops/computers being used will also be encrypted and password-protected. Access to physical research materials/data will also be limited by being stored in locked filing cabinets at DHMC.

Unique identifiers: We will assign a unique identifier to the study information using the numbers provided by NCI/CRCHD/its contractor. For study arm 1 participants, we will link the pre-, post-, and follow-up surveys using the unique identifiers/bar codes. Contact information requested from participants for purposes of follow-up and gift card distribution will be obtained, managed, and stored separately from the other study data. For study arm 2 and 3 participants, the pre- and post- survey data will be collected and stored in the same Qualtrics survey that solicits participant contact information for follow-up and gift card distribution. Only study team members will have access to this file, which has the access restrictions noted above. Once this data is collected via Qualtrics, a study team member will assign a unique identifier to each participant. After initial review of the online data as discussed in section 17.3 for data quality control, subsequent data review and analysis will be performed in a newly created electronic file where participant name and contact information is replaced with the participant's unique, assigned identifier. A separate document will be created consisting of participant name and contact information so that the Qualtrics survey containing participants' other responses does not need to be referenced for participant follow-up and electronic gift card dissemination. Participants asked to participate in follow-up surveys will either be emailed a shortened version of that unique identifier and the month of their original participation as part of the request for their participation in the follow-up and asked to manually enter those two pieces of data into the online follow-up surveys or the study team will use the features within Qualtrics to transfer the participant ID number and month of initial participation to the follow-up surveys so that it automatically populates to avoid the risk of participant error in transferring the code and month to the follow-up surveys. If these Qualtrics features are used to transfer the participant code and month of enrollment information, within Qualtrics there will be a way to trace the data collected at follow-up back to the initial survey in which participants provide their names and contact information (e.g. phone, email, address); however, only study team members will have access to these Qualtrics files. For all study participants, the key linking participants' identities and contact information to their unique identifier codes will be stored separately from other data.

17.3. Data quality control:

The DCC research team will review data collected from the first 5-10 respondents with each Facebook advertisement wave that is launched to check for possible problems such as errors in computer display to participants, errors in skip logic, and robotic responses. If the audit reveals a potential data quality issue, the research team will review additional data to determine how widespread the issue

PROTOCOL TITLE: *Screen to Save 2*

is and will work with the appropriate D-H and DCC colleagues (e.g. tech support) and NCI/CRCHD to address the issues, as needed.

As with any study that collects information about health, such as a person's family health history, it is important to secure this information. As stated below, multiple safeguards have been put in place to minimize the risk of possible data disclosures. We do not plan to obtain a certificate of confidentiality.

17.4. Original paper research forms/data will be kept in a locked filing cabinet at DHMC for five years. All electronic files will be stored on password-protected, encrypted computers that are property of the Dartmouth Cancer Center. Electronic data will also be stored in password-protected sites/applications supported by Dartmouth/DH, such as Qualtrics and Sharepoint/One Drive; access will only be granted to official study team members. All files, paper and electronic, at DHMC will be destroyed six years after the study is completed.

De-identified survey copies/survey data from the experimental arms will be emailed/mailed to NCI/CRCHD/its contractor for data processing on a quarterly basis. Data collected from participants to be shared include pre-test, post-test, and follow-up survey responses (all de-identified, using unique identifier) from our experimental arms (not control arm). We will also provide NCI/CRCHD/its contractor with general information about the in-person events (e.g., dates, locations, number of attendees), about the social media ad reach/metrics, and, as needed, cost. The study coordinators will be responsible for sharing the data with NCI/CRCHD/its contractor. Please see the attached document from NCI/CRCHD entitled *Screen to Save Data Collection Storage and Security* for additional information.

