1.0 Study Summary

Study Title	Screen to Save 2
Study Design	Prospective Observational/Cohort Study Pre-/Post-/Follow-up (via surveys)
Primary Objective	Implement and evaluate Screen to Save (S2S) outreach and educational activities to improve knowledge of colorectal cancer screening methods, to increase intent to get screened for colorectal cancer, and connect screening services to 45-74 year-old residents living in NH and VT—focusing on the most rural counties (RUCC 7—9).
Research Intervention(s)	Education about colorectal cancer screening via online video and written education materials.
Study Population	
The target population is adults aged 45-74 years old who reside in rural New Hampshire or Vermont; “rural” = Rural Urban Continuum Codes (RUCC) 7—9 counties (Coos and Sullivan County, NH; Caledonia, Windsor, Windham, Orange, Orleans, Lamoille, and Essex County, VT)
 
To be eligible to enroll in the study, people must meet the following eligibility criteria:
 
-Be a resident of one of the RUCC 7—9 counties in NH and VT and-Be 45-74 years-old at the time of enrollment 
except in the instance of recruitment via Experimental Arm 4 (e.g. recruitment through Little Rivers Health Care, Inc.), in which case individuals may enroll in the study if age 45-74 and if residing in states or counties other than those specified above, if agreed upon by the research study team and partner institution

Sample Size	Our target recruitment size is 196-225 participants completing the pre/post survey in each of two arms (Arms 2 and 4). Recruitment into study arm 3 will be discontinued in April 2021 due to changes in lung cancer screening guidelines affecting the educational intervention content, resulting in fewer than 196 participants completing that arm. Projecting that up to 50% of people who consent may not complete the pre/post survey, we project that up to 950 people may be enrolled total.
Study Duration for individual participants	Up to 7.5 months
Study Specific Abbreviations/Definitions	S2S= Screen to Save CRC= Colorectal Cancer LCS= Lung Cancer Screening NCI= National Cancer Institute CRCHD=Center to Reduce Cancer Health Disparities (a division of the National Cancer Institute) NON= National Outreach Network (an effort of CRCHD) CHE= Community Health Educator

PROTOCOL TITLE: *Screen to Save 2*

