2.0 Objectives*

2.1 The primary purpose of this project is to: (1) contribute to a nation-wide initiative to educate the public about colorectal cancer risk factors and colorectal cancer screening, (2) evaluate the effectiveness of education about colorectal cancer in changing knowledge, behavioral intentions, and behaviors related to colorectal cancer screening and prevention.

Aim 1: Implement and evaluate Screen to Save (S2S) outreach and educational activities to improve knowledge of colorectal cancer and colorectal cancer screening methods, to increase intent to get screened for colorectal cancer, and connect screening services to 45-74 year-old residents living in NH and VT—focusing on the most rural counties (RUCC 7—9 designations- see figure 1). The study utilizes web-based module to conduct targeted outreach about colorectal cancer screening using the S2S framework and materials and refer them to locally-available screenings, healthcare provider system, and/or healthcare coverage systems.

2.2 Hypotheses:

Online/video outreach about CRC will be effective in: a) increasing adults' knowledge of CRC risk factors, CRC screening recommendations and options, and CRC prevention; b) increasing unscreened adults' intent to get screened for CRC

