6.0 Procedures Involved*

6.1—6.5. This study uses a pre/post/follow-up design utilizing surveys. See below for more information about the surveys.

Our CHE will use a web-based educational-format with video and accompanying educational information shared through social media outreach to conduct a similar intervention as described in experimental arm 1. Recruitment will be facilitated through paid advertisements in Facebook, which will be targeted to 4574 year-old residents in RUCC 7, 8, and 9 counties throughout VT and NH. The advertisements will ask the prospective participants to click to 'learn more' and will be directed to a Qualtrics survey, which will lead them through:

- a- A consenting process utilizing the research information sheet (see enclosed information sheet and waiver of signature).
- b- Screening for eligibility- Prospective participants will be asked a) to select the age group that they are part of; b) Which state they live in; and c) Which county they live in. Participants indicating that they are between the ages of 45—74 years old and live in one of the nine RUCC 7—9 counties in NH and VT will be eligible. Prospective participants will be required to answer the eligibility screening questions in order to advance to the remainder of the study content: the rest of the survey and educational intervention. Participants who do not meet eligibility criteria will be informed that they do not meet the eligibility criteria.
- c- A pre-test survey - Answering pre-test and post-test knowledge questions about colorectal cancer and screening and colorectal cancer behavior intentions questions will be required in order for participants to progress through the study, as will answering a question about the participant's age in years. Answering all other demographic questions and questions about

PROTOCOL TITLE: *Screen to Save 2*

personal or family health experiences will either be required with a “decline to answer” option or optional. Some online questions (i.e. lung cancer and colorectal cancer knowledge questions) will be presented in a random order using Qualtrics features for randomization.

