10.0 Subject Population*

10.1. The target population is adults aged 45-74 years old who reside in rural New Hampshire or Vermont; “rural” = RUCC 7—9 counties (Coos and Sullivan County, NH; Caledonia, Windsor, Windham, Orange, Orleans, Lamoille, and Essex County, VT).

10.2. To be eligible to enroll in the study, people must meet the following eligibility criteria:

- Be a resident of one of the RUCC 7—9 counties in NH and VT and
- Be 45-74 years-old at the time of enrollment

We have three eligibility screening questions that will be asked of all study participants:

- 1) What is your age? (in years)
- 2) What state do you live in?
- 3) What county do you live in?

Participants will be social media users. Social media advertising features will be used to target social media users in the appropriate age range and geographic locations of interest.

PROTOCOL TITLE: *Screen to Save 2*

10.3 Regarding adults unable to consent: For online participants, there are several steps involved in accessing our study which, we feel, will safeguard adults unable to consent from participating in the study; for example, in order to access the study online, that will require having a social media account, navigating away from the social media account to our survey site, reading the information sheet, and proceeding forward to the survey.

Regarding individuals who are not yet adults: All participants will be screened to self-disclose whether they are in the study age range (45-74 years old) at the time of enrollment; hence, no minors will be enrolled. Further, recruitment for the web/video arms (intervention and control) will use Facebook's marketing features to target account holders in the age range of interest to the study.

Pregnant women: Given the 45-74 age group targeted by this study, it is possible but unlikely that pregnant women will be participating. Any inclusion of pregnant women will be strictly incidental and will not present any added risk should they choose to participate. We will not be asking any questions pertaining to pregnancy, and we will not specifically be targeting pregnant women. Regardless of whether or not a 45-74 year-old person is pregnant, receiving age-appropriate cancer screening education and discussing screening options with a medical provider can be beneficial, which is exactly what our study aims to provide and encourage. As such, we will not exclude pregnant women from participating.

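### Section 17.1 attaches its 80% power to a difference-in-difference for which the current design has no stated comparator, leaves the SD undefined, and the completer target is given both per arm and without arms

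*Combined protocol and SAP*

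**What the plan says.** The only power statement is in Section 17.1 of the combined protocol and SAP. It specifies a two-tailed test at the 0.05 level with "80% power to detect an effect size of 0.2 (20% difference in the before/after difference-in-difference estimates), with a standard deviation of 1.0". The section gives no sample size, number of groups, allocation ratio or pre/post correlation. It adds that "changes will be look at across groups" and does not name the groups.

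The numbers appear elsewhere, in two forms. The Study Summary (Section 1.0) asks for "196-225 participants completing the pre/post survey in each of two arms (Arms 2 and 4"), allows for up to 50% non-completion, notes that Arm 3 closed with fewer than 196 completers, and concludes that "we project that up to 950 people may be enrolled total". Section 12.0 says "Our target recruitment size is 196-225 people completing the pre/post survey" and mentions no arms.

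The hypotheses in Section 2.2 begin "Online/video outreach about CRC will be effective in" and go on to increases in knowledge and in screening intent; neither is a contrast between groups. Section 6.0 describes a pre/post/follow-up survey design. The entry for revision 15 describes the simplified protocol as a single intervention with surveys before and after it.

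**The concern.** A difference-in-difference compares the change in one group with the change in another. The hypotheses, the procedures and the description of the intervention supply only one group's change. The stated power therefore belongs to an estimand that the current design does not define.

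Two things are at stake. First, a reader cannot tell which analysis has 80% power. If a result across groups is reported, Section 17.1 could be taken to give that comparison 80% power, and a null finding could be over-read. Second, a reader cannot tell whether the plan was for 196-225 or 392-450 completers, and so cannot judge whether the target was met. Revision 15 was filed to support results reporting, so this is the text against which the results will be read.

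**Working it through.** **Inputs.** From Section 17.1: two-sided alpha 0.05, power 80%, effect 0.2, SD 1.0. From the Study Summary: 196-225 completers in each of two arms, up to 50% non-completion, up to 950 enrolled, fewer than 196 completers in Arm 3. From Section 12.0: 196-225 completers. Equal group sizes are assumed for the two-group calculations. No pre/post correlation (rho) is stated, so any value below is an assumption.

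**Reproducing 196.** (1.960 + 0.8416)² = 7.849. For a one-group paired test with SD of change 1.0:

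n = 7.849 × 1.0² / 0.2² = 7.849 / 0.04 = 196.2 (198.2 with the t distribution).

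This matches the lower end of the target. Paired t-test power is 79.6% at 196 and 84.8% at 225.

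**The same inputs as a two-group difference-in-difference.** With SD of change 1.0 in each group:

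n per arm = 2 × 7.849 / 0.04 = 392.4, so about 393.

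Power by two-sample t-test is 50.6% at 196 per arm and 56.2% at 225 per arm. The difference detectable with 80% power is 0.284 SD and 0.265 SD respectively.

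**Other meanings of SD 1.0.**

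- *SD of the between-group contrast of changes.* Then 2 × (SD of change)² = 1, so the SD of change is 0.707 and n per arm = 2 × 7.849 × 0.5 / 0.04 = 196.2. Power is about 80% at 196 per arm and 85% at 225.
- *SD at each time point.* The SD of change is √(2(1 − rho)). At rho = 0.75 this is again 0.707, giving 196.2 per arm for two groups. At rho = 0.5 it is 1.0, which returns the 393 per arm above. One-group power at 196 is 50% at rho 0, 80% at rho 0.5 and 95% at rho 0.7.

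So 196 arises from a one-group test under one SD definition and from a two-group test under others. Section 17.1 does not say which was used.

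**Enrolment at 50% completion.**

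| Reading of 196-225 | Enrolled, before Arm 3 | Room for Arm 3 within 950 |
|---|---|---|
| Per arm, two arms | 392 / 0.5 = 784 to 450 / 0.5 = 900 | 166 to 50 enrolled, i.e. 83 to 25 completers |
| Total | 196 / 0.5 = 392 to 225 / 0.5 = 450 | more than enough for any Arm 3 size below 196 completers |

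With the most Arm 3 could contribute (195 completers, 195 / 0.5 = 390 enrolled), the total reading reaches 450 + 390 = 840, still within an upper limit of 950.

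**The case against.** The strongest reply is that the SD of 1.0 follows directly after the difference-in-difference phrase and may describe that contrast. On that reading 196 per arm is correct, matches the Study Summary's per-arm wording, and gives about 80% power. This stands as a possibility. A reader might infer that 196 can only be a one-group paired calculation, but the documents do not support that: the paired reading also needs an unstated definition, namely that 1.0 is the SD of change. What survives is that neither reading can be confirmed from the text, and that the contrast reading still needs a comparator that the current design does not identify.

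A reader might also infer that the 950 projection proves the per-arm target. It does not. Arm 3 enrolment is not stated, and a total of 196-225 plus Arm 3 also stays below 950. The per-arm reading is the more natural one, because the projection follows the per-arm figure in the same entry and comes closer to 950.

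Finally, it can be said that nothing practical turns on this, since no test of Arm 2 against Arm 4 is specified and recruitment can no longer change. The first half is right: it would be wrong to say that a planned between-arm test has only 51-56% power. That figure is conditional on such a comparison being reported and on 1.0 being the SD of change. But Section 17.1 leaves the comparison open without naming the groups, and the discrepancy in the target remains in any case.

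**Conclusion.** The point holds as a mismatch and an omission, not as proof of a wrong calculation. The stated power is tied to a difference-in-difference, while the current hypotheses and procedures describe within-group change in one intervention.

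If 1.0 is the SD of change, the 196-225 target gives about 80% to 85% power for the within-group test, so the analysis that the design supports may well be adequately powered. The same inputs give only about 51% to 56% for a two-arm comparison of change at that size per arm. If 1.0 is the SD at each time point, within-group power at 196 runs from 50% to 95% over assumed correlations of 0 to 0.7. Describing the effect as a 20% difference adds to the ambiguity, since that is not the same thing as 0.2 SD.

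Independently of the SD question, Sections 1.0 and 12.0 state targets that differ twofold if Section 12.0 is read as a total, and both are current text. This should be fixed, but it biases no estimate. Leftover wording about arms and a control group elsewhere, for example in Sections 6.0 and 10.3, is editorial clean-up and not part of this point.

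**What to change.** 1. In a dated correction to Section 17.1, the sponsor confirms which test and which SD the 196 was calculated for. The paired calculation should not be entered as the historical rationale unless the sponsor confirms it.
2. State power for the analysis that the current design supports: a two-sided 0.05-level paired test of pre/post change within one group, for a mean change of 0.2 SD, with power about 80% at 196 and 85% at 225 if 1.0 is the SD of change. Otherwise give the power under the confirmed SD and correlation. Name the outcome to which it applies.
3. Do not attribute the 80% to a difference-in-difference unless a comparator and an SD definition are stated. Express the effect in SD units, not as a percentage.
4. Either name the groups to be compared, label that comparison exploratory and give its own power (about 51% to 56% at 196-225 per arm if the SD of change is 1.0), or delete it.
5. Reconcile Sections 1.0 and 12.0 to one target, per arm or total, and restate the enrolment projection to match, including participants already enrolled in Arm 3.

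The cost is wording in Sections 1.0, 12.0 and 17.1, plus the sponsor's confirmation of the original calculation. No further participants are needed. The drawback for the sponsor is that the stated power for any comparison across groups may be less favourable.
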